Peer support in a healthcare context is an explicit form of social support established to provide individuals with emotional, appraisal, and informational support by another person living with a similar condition (5). A systematic review of peer support for parents of children with chronic disabling conditions found that parents benefited from a shared social identity, supporting and learning from experiences of others, and personal growth (6). However, little research exists on parent peer support in JIA and families face numerous barriers to accessing in-person social support specific to JIA. Providing peer support online is an innovative approach to improve the *accessibility* and *acceptability* of peer support programs for parents of children newly diagnosed with JIA.

Preliminary Work

The iParent2Parent Program is based on the collective research and clinical expertise of the team and *patient expressed interest* in a parent peer support program. Both the structure of the iParent2Parent Program and the parent peer mentor training was systematically developed based on: (a) a theoretical framework for peer support interventions in health care contexts (5); evidence of successful parenting interventions in other chronic health populations (6-8); (c) adaption of The iPeer2Peer Program, an established and successful online peer mentor program and peer mentor training program for adolescents and young adults with JIA (9, 10); (d) adaptation of the Cassie and Friends Parent to Parent Support Program (CF-PSP) for parents of children with rheumatic conditions. The CF-PSP has formalized parent mentor training as well as the process of matching parents who would benefit from peer support with another parent who also has a child with a rheumatic condition. The iParent2Parent Program capitalizes on lessons learned from the development of other peer mentoring programs to create an accessible and acceptable program for parents of children newly diagnosed with JIA.

Objectives: To develop a parent peer mentoring program, the iParent2Parent Program, that is

feasible and effective for parents of children living with JIA. This proposal is part of a phased approach to develop online peer mentoring interventions:

Phase 1 (completed): The iParent2Parent Program is based on our previously developed peer mentoring programs: iPeer2Peer Program and CF-PSP (9, 10).

Phase 2 (current proposal): The feasibility of the online iParent2Parent Program for parents of children living with JIA will be evaluated in a pilot randomized controlled trial (RCT).

Phase 3 (future proposal): Results of the pilot RCT will inform the refinement of the iParent2Parent Program and determine the appropriate sample size for a future large-scale RCT comparing the effectiveness of the iParent2Parent Program to a waitlist control group across Canada.

Methods

Specific Aims: This pilot RCT will test the feasibility of the iParent2Parent Program for parents of children diagnosed with JIA. Using implementation outcomes, measures of feasibility will be evaluated and estimates of effect size and variance will be assessed for parent QOL, perceived social support, coping, and parenting stress. Estimates of effect size and variance will inform sample size of a future multisite RCT.

Research Questions:

- I. Primary implementation: Can the iParent2Parent Program be implemented as planned with respects to: (a) what are the accrual and dropout rates? (b) can the program, control, and outcomes measures be deployed as planned (fidelity)? (c) what are parent perceptions regarding program acceptability and satisfaction? and (d) what are the levels of program engagement?
- II. Secondary potential mechanisms of effectiveness: What are the estimates of treatment effect sizes and variance in QOL, perceived social support, coping, and parenting stress, in parents of children diagnosed with JIA who complete the iParent2Parent Program versus a waitlist control group?
- III. Exploratory: Does involvement in the iParent2Parent Program lead to differences in peer mentors' QOL, perceived social support, coping, and parenting stress? What are the perceptions of peer mentors regarding the benefits and challenges of the iParent2Parent Program?

Description of Study Population:

Peer Mentor Criteria.

Inclusion Criteria:

- (a) English-speaking caregiver of a child with JIA
- (b) Nominated by their child's health care team as a good candidate to act in the mentor role, including parents who manage the demands of having a child with JIA, and have low risk factors (no history of mental illness).

Exclusion Criteria:

- (a) Significant cognitive impairment or major co-morbid illness of parent that impedes ability to provide the program (e.g., psychosis, active suicidal ideation, cognitive delays that would impact ability to participate and complete questionnaires)

Note: every effort will be made to recruit a diverse group of parent mentors (e.g., parents of children with various subtypes of JIA, parents who live in rural vs urban settings, various ethnicities).

Mentee Criteria.***Inclusion Criteria:***

- (a) English-speaking caregiver of a child diagnosed with JIA according to ILAR criteria (11) prior to their 18th birthday
- (b) access to computer capable of using free Skype software. *Note:* 85% of Canadian households have high speed Internet availability as of 2010 (12).

Exclusion Criteria:

- (a) Significant cognitive impairment or major co-morbid illness of parent that impedes ability to engage in program (e.g., psychosis, active suicidal ideation, cognitive delays that would impact ability to participate and complete questionnaires)

Study Design:

A waitlist pilot RCT design using central randomization with repeated measures will be used to evaluate the feasibility of the iParent2Parent Program. Up to 12 peer mentors will be enrolled across two large tertiary pediatric rheumatology centres (SickKids and IWK Health Centre). A total of 40 consenting parents of children diagnosed with JIA will also be enrolled from two large tertiary pediatric rheumatology centres (SickKids and IWK Health Centre) and randomized to the experimental (iParent2Parent Program) (n=20) or control (waitlist) (n=20) group. The decision was made not to recruit at BC Children's Hospital in order to prevent contamination of the sample given the pilot CF-PSP is currently being evaluated in the rheumatology clinic. BC Children's will be recruiting in the future RCT.

Experimental Group. In addition to standard medical care provided to their child, parents in the experimental group will receive online peer mentoring via the iParent2Parent Program. The iParent2Parent program is a tailored peer-mentorship program that provides modeling and reinforcement by peers (trained parents of children with JIA) to parents of children diagnosed with JIA. The program will run over 2-3 months via 5-10 weekly to bi-weekly Skype calls. [name] will identify 5-7 suitable mentors (male and female) per site who meet eligibility criteria. A member of the research team will interview interested mentors, describe the program, outline requirements, and answer any study-related questions. During mentor training, all mentors will meet with [name], a licensed psychologist, who will screen for potential psychosocial concerns and considerations when taking on the role of a mentor (e.g., the personal impact of discussing their own child's JIA, speaking with other parents who have a child with JIA). Efforts will be made to pair mentors and mentees who share similar characteristics (e.g., sex/gender) as well as their child's characteristics (e.g., age, diagnosis). During the study period, mentors may be assigned up to 3 mentees at any time. The total number of mentees a peer mentor takes on is their choice. Mentees may be from either SickKids or IWK Health Centre. Before assigning a mentee, the research coordinator will reach out to the peer mentor to discuss additional commitment and assign mentees based on availability and willingness of mentors. A research assistant (RA) at each participating site will facilitate initial Skype calls. Dyads will be responsible for scheduling remaining calls at mutually agreeable times (same time each week with flexibility to schedules). Mentors and mentees may coordinate future calls via Skype or email. If participants cannot complete the iPeer2Peer intervention via Skype (e.g., no access to computer and/or internet), a phone option will be made available for participants to take part in the program.

Parent Mentor Training. Parent mentor training will involve a stepwise approach including both self-directed in-home training and one full day of in-class training facilitated by a psychologist [name] and social worker [name]. In-class training will comprise of lectures, active group discussions, small group activities, and role-play activities. iParent2Parent call topics will be decided by the mentor and mentee. However, the training manual will include suggested topics,

advice on structuring conversations, and guides to redirect conversations. Based on the evidence on parent outcomes (6-8), training will emphasize active listening, fostering adaptive coping, and problem-solving skills. Peer mentors will have access to research staff for additional training and support throughout the duration of the study if needed. This includes consultations with research staff and additional training in mentorship skills.

The following study safeguards will be put in place and any adverse events will be tracked:

- Peer mentor training on confidentiality, boundaries, self-care, and when to seek support.
- Peer mentors will be assigned a study specific online account and email address to encourage appropriate boundaries between mentor and mentee.
- Peer mentor training on emergency identification and reporting using a standardized concerns checklist, appropriate services (e.g., 911), and/or the study or local health care team.
- A member of the research team will contact peer mentors at least bi-monthly to ensure mentors are comfortable in their role, not experiencing any undue stress, and to discuss any concerns with the program.
- [name] will be available to facilitate appropriate referrals as necessary via social work department at SickKids and IWK Health Centre.

Control Group. The control group will be on a waitlist and receive usual care without intervention. The iParent2Parent Program will be offered after completion of all outcome measures.

Both Groups. Primary and secondary outcome measures will be collected online from both groups at baseline, 3 months, and 6 months.

Peer Mentors. Prior to mentor training, mentors will complete baseline outcome measures. Immediately following training, mentors will complete training evaluations. At study end, mentors will complete follow-up outcome measures and participate in a focus group.

Procedure:

Following ethics approval, eligible parents will be invited to take part in this study by the clinical care team in the rheumatology clinics at SickKids and IWK Health Centre. Participants may also self-identify to the research team by responding to the study posters or postcards that are in the clinics. A site-specific clinical research project coordinator (CRPC) will obtain consent from interested parents. A member of the research team will track the number of eligible parents approached and if voluntarily provided, reasons for refusal. Subsites will be responsible for consenting mentee participants locally. Once informed consent is obtained, the subsite RA will send mentee contact information to SickKids via secure file transfer. A master database of all participants will be housed at SickKids as we are the central hub and primary point of contact for recruitment and study activity.

Once consent is obtained, baseline demographic and disease-related data will be collected from the child's medical charts and pre-intervention measures will be administered online to parent participants. Online measures for this study will be obtained using REDCap (Research Electronic Data Capture) and housed on a secure server.

Randomization: The CRPC will enter participant ID and stratification variables (i.e., disease activity and study centre) for group allocation into a secure, web-based randomization software (Randomizer). Participants will be randomized 1:1 into one of two groups (iParent2Parent or waitlist), and allocation will remain hidden. The CRPC will then contact participants to inform them of group assignment and instruct them on procedures to be followed.

Proposed Methods for Protecting against Sources of Bias

Blinding. The randomization process will be blinded to site-specific staff and co-investigators to reduce the chance of experimenter bias. Mentors and mentees will be asked not to discuss their study involvement with others until study completion. Mentors and mentees will complete all outcome measures online.

Contamination. To minimize the small potential risk of contamination, participants will be asked about their involvement in other peer support groups, other peer mentors, or any other concomitant interventions.

Outcomes Measures:

- **Primary Outcome:** trial feasibility and acceptability of the iParent2Parent Program. Criteria for feasibility are based on studies previously conducted by our group and will be: accrual rate of >70%, attrition rate of <15%, technical difficulties reported by <10% of parents and mentors, adherence rate of >80%, <5% missed responses on outcome measures and high acceptability (based on qualitative analyses). Data related to the primary outcome will be recorded on investigator-developed forms. Acceptability data will be collected using semi-structured interviews with mentors and mentees at end-of-study.
- **Secondary Outcome:** determination of treatment effect estimates for mentee participants. Effect sizes will be determined for the following: QOL (PROMIS Adult Profile 25 (13), perceived social support (Short form versions of the PROMIS battery for: Social Isolation; Informational Support; and Emotional Support) (13), coping (Coping Health Inventory for Parents (CHIP)(14); and parenting stress (Parental Stress Scale (PSS) (15).
- **Exploratory Outcome:** determination of impact for peer mentors. Effect sizes will be determined for the following: QOL (PROMIS Adult Profile 25) (13), perceived social support (PROMIS Social Isolation; Informational Support; Emotional Support) (13), coping (CHIP) (14), and parenting stress (PSS) (15). Peer mentor perceived benefits and challenges will be collected qualitatively using semi-structured interviews with mentors at end-of-study. Both groups will be asked about additional peer support sought during these time periods.

Statistical Plan:

Feasibility. This project builds on previous and ongoing research conducted by the research team. Our multidisciplinary team comprises of an experienced group of investigators with extensive and collective depth of clinical and research expertise in JIA, parenting chronically ill children, eHealth, QOL, peer support, knowledge translation, qualitative analysis, and mixed methods research.

Sample Size and Recruitment. A total of 20 participants per group is suggested for recruitment in pilot studies to examine intervention feasibility (16). SickKids and IWK Health Centre see over 150 new pediatric JIA diagnoses per year. Using a conservative estimate of 75 children diagnosed in 6 months, with a 30% refusal rate (based on our previous work (17)), we will recruit 40 parents within the timeframe.

Quantitative data will be analyzed using SAS 9.1.3. Baseline sample characteristics will be summarized. Rates of accrual, attrition, adherence, and missing data with 95% confidence intervals will be calculated. To inform sample size calculations for a larger trial, data will be analyzed as a larger trial and estimates of variance and correlation on secondary and exploratory outcome variables will be estimated. If assumptions for parametric statistics are met, linear mixed models will be used to test intervention effects on all outcomes. We will adjust for important factors such as child age, sex, and number of mentoring sessions in our model. Covariance structure will be selected based on model diagnostic statistics. We will examine patterns of missing data, determine demographic and/or clinical characteristics that are related

to missing data at each time point, and the potential impact on the primary findings. The semi-structured mentor and mentee interviews will be audio-recorded and transcribed verbatim. All transcripts will be verified against recordings and imported into NVivo10. Data will be analyzed using an inductive qualitative content analysis approach (18, 19) and used to refine the intervention before a large-scale RCT. This analytic approach was used in previous RCTs and our research team has the required expertise in qualitative analysis (20, 21).

Impact

Expected Results:

This proposal directly impacts an under-researched area of psychosocial and familial health outcomes in pediatric rheumatology. It will result in the development of a new online peer mentoring program for parents of children with JIA. The results of this pilot study will be leveraged in two significant ways: 1) to apply for a large-scale multi-site grant investigating effectiveness and implementation outcomes of the iParent2Parent Program across Canada; and 2) the iParent2Parent Program will be made adaptable to other childhood rheumatic diseases.

Project Deliverables:

This proposal builds from a strong foundation of collaborations and previous experience developing peer mentorship programs for adolescents with JIA (see Preliminary Work section). This project capitalizes on existing research and clinical knowledge to develop a structured program and manual that other pediatric centres can adopt. The iParent2Parent manual will be created as a standalone resource for selection and training peer mentors as well as how to structure the iParent2Parent Program.

Dissemination Plan:

Knowledge translation approaches will include both active and passive strategies in all research stages that involve key stakeholders, including pediatric rheumatology groups (e.g., CAPRI, CARRA), NGOs (Cassie and Friends, The Arthritis Society), lay consumers, clinicians and scientists. Results will be disseminated through key national and international conferences, public affairs and scientific-style newsletters, and publication in leading open-access journals. Findings will also be shared with patients and consumer groups (1-page brochure, media releases [newspaper, magazines, social media such as Twitter], and posting on key websites [e.g., hospitals]).

Feasibility and Sustainability

The sponsor/funder of this research is SickKids and the Canadian Rheumatology Association / Canadian Initiative for Outcomes in Rheumatology Care.

Research Team:

[name] is the lead investigator of this study and is a health clinician scientist and psychologist at SickKids and an Assistant Professor at the University of Toronto. She will oversee every aspect of this trial and its conduct, including day-to-day management of the trial and development of training manuals. **[name]**, a clinician scientist and nurse with expertise in mixed methods research, is [name] career mentor and will support [name] in all aspects of this study for the duration of this grant. **[name]**, are pediatric rheumatologists and will act as site investigators overseeing site specific screening and recruiting of parent peer mentors and parent mentees and controls for this project. Two investigators from BC Children's Hospital, **[name]**, a social worker in rheumatology, and **[name]**, a pediatric rheumatologist, will support the development and facilitation of the parent mentor

training and provide expertise related to the CF-PSP. All members will attend meetings to plan and monitor the trial, interpret findings, and write final reports.

Limitations and Identified Alternatives:

Inherent challenges exist when developing a new program, and this has guided our decision to focus on a feasibility RCT. The iParent2Parent Program may not be suitable for all parents of children diagnosed with JIA. Some families in rural communities do not have access to sufficient Internet bandwidth to run Skype. Efforts will be made to adapt the program (e.g., allow phone participation) for all interested parents to participate. The iParent2Parent Program is also time intensive. To accommodate this potential barrier, we have included flexibility in the number of calls between mentors and mentees. There is a potential that mentor-mentee dyads are not well suited for each other. In these cases, we will re-match a mentee with a different mentor. Mentors may also choose to discontinue the program. We will over-recruit a pool of mentors to control for drop out and variability in age, gender and child subtype of JIA. We cannot guarantee our sample will be representative of the whole parent population. However, we are recruiting from two tertiary care pediatric hospitals in ethnically diverse locations that serve both urban and rural populations.

Timeline

The proposed study will be completed within 2 years.

	YEAR 1				YEAR 2			
	Q1	Q2	Q3	Q4	Q1	Q2	Q3	Q4
Pre-intervention								
Study set-up	x	x	x	x				
Program adaption	x							
Mentor recruitment				x	x			
Mentor training workshop					x			
Participant recruitment					x	x	x	
Participant data collection					x	x	x	
Intervention								
Participant data collection					x	x	x	
Post-Intervention								
Participant data collection					x	x	x	
Participant interviews/focus groups					x	x	x	
Data analysis							x	x
Control group offered intervention							x	x
Knowledge Translation								
Presentations								x
Final reports & manuscript								x
Research team meetings	x	x	x	x	x	x	x	x

Project Leverages

This project leverages collaborations and phased methodology of the successful development of the iPeer2Peer Program. The iPeer2Peer Program has, based on *patient expressed interest*, already been adopted nationally and internationally (USA: Arthritis Foundation, Ireland: iCAN). The iPeer2Peer Program has also been expanded and is being tested in pediatric samples living with cancer, inflammatory bowel disease, chronic pain, sickle cell disease, and

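### Specific Aims uses the pilot's effect size to size the next trial, the statistical plan does not, and effects are to be tested on all outcomes with 20 per arm

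*Protocol*

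**What the plan says.** Three places in the Protocol describe what the pilot hands to the next trial.

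- Specific Aims (Methods): "Estimates of effect size and variance will inform sample size of a future multisite RCT".
- Objectives, Phase 3: the pilot's results are to "determine the appropriate sample size for a future large-scale RCT".
- Statistical Plan, quantitative paragraph: to inform that calculation, "data will be analyzed as a larger trial", and "estimates of variance and correlation on secondary and exploratory outcome variables will be estimated". Effect size is not named here.

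The same paragraph adds that, if parametric assumptions hold, "linear mixed models will be used to test intervention effects on all outcomes".

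The sample size rests on a literature citation about feasibility: "A total of 20 participants per group is suggested for recruitment in pilot studies to examine intervention feasibility (16". On allocation, "Participants will be randomized 1:1 into one of two groups (iParent2Parent or waitlist". No alpha, power, target difference or precision is given for any between-group comparison, and no sentence marks the tests as descriptive.

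**The concern.** There are two linked problems.

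First, the protocol gives two different accounts of what the pilot supplies to the sample-size calculation. The statistical plan's account (variance and correlation) is sound. The Specific Aims add effect size, which 40 parents cannot estimate closely enough to serve as a design value. An estimate that is too high by chance leads to a next trial that is too small; one near zero or negative gives an impractical number or none.

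Second, testing every outcome in a sample justified only by feasibility will often miss a moderate real effect, and it leaves room for a chance significant result. That matters somewhat more because the Project Leverages section foresees rapid adoption should the program prove feasible and effective.

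**Working it through.** **Inputs from the Protocol.** 20 per arm, 1:1. At least six secondary scores (Outcomes Measures): PROMIS Adult Profile 25 counted as one, three PROMIS social support short forms, CHIP and PSS. Two follow-ups, at 3 and 6 months. Feasibility limit: "attrition rate of <15" per cent; at 15%, 20 × 0.85 = 17 per arm remain.

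**Assumptions, because the Protocol states none.** Two-sided 0.05, 80% power for the next trial, a simple two-group comparison, standardised difference *d*.

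**The plan's own figure.** The 20 per group has no formula to reproduce. The recruitment arithmetic is consistent: 75 × (1 - 0.30) = 52.5, which covers 40.

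**Precision of the pilot effect size.** Exact intervals come from the noncentral t distribution with 38 df. The approximation d ± 1.96 √(2/n + d²/4n) gives nearly the same. For d = 0.30: 1.96 × √(0.1 + 0.0011) = 0.62.

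| Observed d | n per arm | Exact 95% CI |
|---|---|---|
| 0.30 | 20 | -0.33 to 0.92 |
| 0.50 | 20 | -0.13 to 1.13 |
| 0.50 | 17 | -0.19 to 1.18 |

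**Implied future sample size.** n per arm = 2(1.96 + 0.8416)²/d² = 15.70/d².

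- d = 0.30 gives 175; d = 0.50 gives 63.
- Upper limits: 15.70/0.92² = 18.5, so 19; 15.70/1.13² = 12.3, so 13.
- Both lower limits are below zero, so no finite n exists there.

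**Sizing the next trial on the pilot d alone** (simulation of 200,000 pilots, 20 per arm):

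| | True d = 0.30 | True d = 0.50 |
|---|---|---|
| Pilot d ≤ 0, no n derivable | 17% | 6% |
| Of the rest: real power under 80% | 61% | 53% |
| Of the rest: real power under 50% | 42% | 27% |
| n per arm: median (10th to 90th percentile) | 114 (28 to 1868) | 57 (18 to 517) |

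**Sizing on a fixed target with only the SD from the pilot.** For a target equal to a true d of 0.50, the median is 62 per arm (46 to 82) and real power is 67% to 89% (10th to 90th percentile). Median power is 79%, so about half of these trials also fall below 80%. The contrast with the table therefore lies in the spread and in the share under 50%, more than in the under-80% row. An upper confidence limit for the SD deals with the remaining shortfall: the one-sided 80% limit is √(38/χ²) with χ² at its 20th percentile on 38 df, that is √(38/30.54) = 1.12 times the pilot SD, or about 24% more participants.

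**Tests in the pilot.** For d = 0.50, noncentrality is 0.5 × √10 = 1.58 and power is 34% (29% at 17 per arm). Significance needs an observed d of at least 2.024 × √(2/20) = 0.64. The chance of at least one false positive, if tests are independent, is 1 - 0.95⁶ = 26% for one test per score and 1 - 0.95¹² = 46% for one per score at each follow-up.

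**The case against.** The strongest reply is that the protocol promises less than it may seem to.

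- The Specific Aims say the estimates will *inform* the sample size. A reader might infer a commitment to enter the observed effect as the design effect; the text does not say that. The Phase 3 sentence refers to the pilot's results in general, which include accrual and attrition. This stands, so the under-powering figures are conditional on the pilot effect being used alone.
- The statistical plan already names the right quantities. This also stands. The repair is to bring the Specific Aims into line with it.
- A reader might infer that the next trial goes ahead only if the pilot's effects look good, which would add selection bias. The documents do not support this: the numerical criteria concern feasibility only, and there is no efficacy rule for proceeding.
- The planned mixed model can be more precise than a t-test. With an assumed baseline correlation of 0.5 or 0.7, the half-width of the interval for d falls from 0.62 to about 0.54 or 0.44, and power for d = 0.50 rises to about 43% or 58%. An observed 0.30 still has an interval that includes zero.
- The scores are correlated self-reports. With an assumed common correlation of 0.3 to 0.7, the false-positive chance drops to about 40% to 23% for 12 tests and 24% to 16% for six. This stands, and 26% and 46% are upper figures.
- Testing is conditional on parametric assumptions, and the secondary research question asks for estimates. That is true, and it makes the plan to test out of step with the protocol's own question.

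**Conclusion.** The point holds as an inconsistency in the protocol plus an analysis aim the sample cannot carry. Effect size is named as a sizing input in one place and left out in another, and with 20 per arm its 95% interval is more than 1.2 standard deviations wide without adjustment. It cannot tell a next trial of under 20 per arm from one that could not be sized at all. Tests on all outcomes have about one chance in three of detecting a difference of 0.50 without adjustment, somewhat more with it.

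These figures rest on assumed alpha, power and true effects, and on a two-group comparison. Baseline adjustment softens them without changing the conclusion. The primary feasibility outcome is not affected, and the future trial would be a separate proposal. What is at stake is how that trial is sized and what is claimed about efficacy from this one.

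**What to change.** - **Specific Aims and Phase 3:** remove effect size as a sizing input so that they agree with the statistical plan. State that the future trial will be powered on a target (minimally important) difference for its chosen primary measure, set beforehand. From the pilot, take only the SD through an upper confidence limit (for example one-sided 80%, about 1.12 times the pilot SD), the correlation, and the consent and attrition rates.
- **Statistical Plan:** replace the plan to test effects with one to *estimate between-group differences with 95% CIs*, and state that no efficacy conclusion will be drawn from significance tests.

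The cost is wording only: participants, visits and measures stay as they are. The downside is that the future sample size may come out larger than a favourable pilot estimate would have suggested.

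### Research Question II defines the secondary effect size in programme completers against an unrestricted waitlist group; this is not the randomised comparison and does not match the outcome and analysis text

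*Protocol*

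**What the plan says.** All places are in the protocol.

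- **Research Questions, II:** the treatment effect sizes and variances for quality of life, social support, coping and parenting stress are sought "in parents of children diagnosed with JIA who complete the iParent2Parent Program versus a waitlist control group".
- **Specific Aims:** "Estimates of effect size and variance will inform sample size of a future multisite RCT".
- **Study Design and Randomization:** 40 parents are "randomized to the experimental (iParent2Parent Program) (n=20) or control (waitlist) (n=20) group". "Participants will be randomized 1:1 into one of two groups (iParent2Parent or waitlist").
- **Experimental Group:** "The program will run over 2-3 months via 5-10 weekly to bi-weekly Skype calls". No number of calls is named as completion.
- **Control Group and Both Groups:** waitlist parents are offered the programme only once their outcome measures are finished. Both arms are measured at baseline and at months 3 and 6, with no condition on calls made.
- **Outcomes Measures:** the secondary outcome is described as effect estimates for the mentees, without mention of completion. The feasibility criteria include "attrition rate of <15" per cent and "adherence rate of >80" per cent.
- **Statistical Plan:** linear mixed models are planned for all outcomes, with no completer restriction. Missing-data patterns are to be examined, and the count of mentoring sessions is listed as a covariate.

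**The concern.** Randomisation makes the two groups of 20 comparable. It does not make a self-selected part of one group comparable with the whole of the other. Whether a parent completes is settled after allocation and may depend on stress, coping or time, which are related to what is being measured. A matching subset of controls cannot be formed, because waitlist parents have no programme to complete while outcomes are being collected. With completion undefined within a range of 5 to 10 calls, the completer group could also be settled after the data are seen.

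What is at stake is the planning value carried into the next trial. That trial is to test effectiveness against waitlist, so it needs the effect of offering the programme, including to parents who stop early. A completer estimate answers a different question and may lead to a wrong sample size.

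**Working it through.** **The plan's own figures.** 2 x 20 = 40, as stated. Recruitment: 75 x (1 - 0.30) = 52.5 parents, which covers 40. The protocol gives no effect size, SD or power, so there is no stated effect to reproduce.

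**The texts side by side.** Research Question II restricts the programme arm to completers. The data-collection, outcome and analysis sections do not. The session-count covariate even suggests that parents with differing numbers of calls stay in the model. The protocol therefore describes two different comparisons.

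**Form of the bias.** Let q be the share of the programme arm that does not complete, and g the outcome gap in SD between completers and non-completers that would exist without any programme effect. Randomisation gives both arms the same expected mix. With no true effect:

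- control mean = (1 - q) x completer mean + q x non-completer mean
- completers minus controls = q x (completer mean - non-completer mean) = q x g

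**Inputs.** q = 0.15 to 0.20 is borrowed from the attrition and adherence criteria. Neither is defined as programme completion, and both are limits rather than expected rates. g = 0.3 to 0.8 SD is assumed.

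- Low end: 0.15 x 0.3 = 0.045 SD
- Middle: 0.20 x 0.5 = 0.10 SD
- High end: 0.20 x 0.8 = 0.16 SD
- g = 0 gives 0. A negative g reverses the sign.

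**Simulation check.** No true effect, 20 per arm, 17 or 16 completers (15% or 20% non-completion); the correlations between tendency to complete and outcome are assumed.

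| Correlation | Completers minus controls | As randomised |
|---|---|---|
| 0 | 0.00 SD | 0.00 SD |
| 0.3 | 0.08 to 0.10 SD | 0.00 SD |
| 0.5 | 0.13 to 0.17 SD | 0.00 SD |

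**Against the pilot's precision.** The standard error of a standardised difference with 20 per arm is about sqrt(2/20) = 0.32 SD, so the 95% half-width is 1.96 x 0.316 = 0.62 SD. The illustrated bias is 0.045/0.316 = 0.14 to 0.16/0.316 = 0.51 of one standard error.

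**Effect on the next trial.** Assume 80% power, two-sided 5%, n per arm = 2 x (1.96 + 0.842)^2 / d^2, and a true as-randomised effect of 0.40 SD.

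- Needed: 2 x 7.85 / 0.16 = 98.1, so 99 per arm.
- q = 0.20, g = +0.5: the completer estimate centres on 0.50 SD, giving 63 per arm. Actual power = Phi(0.40 x sqrt(63/2) - 1.96) = Phi(0.285) = 61%.
- q = 0.20, g = -0.5: the estimate centres on 0.30 SD, giving 175 per arm, more than needed.
- No prognostic gap, but only completers benefit: the as-randomised effect is (1 - q) times the completer effect. A completer effect of 0.40 SD becomes 0.34 (q = 0.15) or 0.32 SD (q = 0.20), needing 136 or 154 per arm. At 99 per arm, power would be 67% or 61%.

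**The case against.** The strongest reply is that a phrase in a research question is not the analysis plan. The sections that govern data collection, outcomes and models contain no completer restriction and no exclusion rule, so the analysis may well include everyone. This stands in part: it shows that the fault is a badly stated comparison in conflict with other sections, not a settled plan to exclude parents. It does not remove the fault, because nothing in the protocol overrides the question as worded.

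Four stronger readings are tempting, and the documents do not support them.

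- *The effect will be inflated and the variance reduced because the most burdened parents drop out.* The protocol does not say who stops. Its limitations section acknowledges the time demand, but answers it with a flexible number of calls, re-matching of dyads and telephone participation. Parents who feel little need could equally stop early.
- *Three or four of 20 programme parents will be discarded.* That rests on the borrowed 15-20% and on an exclusion that the Statistical Plan never specifies.
- *The lack of an intention-to-treat statement is itself a defect.* The analysis population may be set in a statistical analysis plan that is not shown. Only the wording that is present can be faulted.
- *The bias is as large as q x g.* That formula compares raw follow-up means. The design has baseline measures and repeated-measures models; if baseline is used, part of any stable gap is removed.

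It is also fair to say that this is a secondary aim of a small pilot, and that the illustrated bias is small beside sampling error. Bias does not average out as sampling error does, but its size here does not justify alarm.

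**Conclusion.** The point holds as a fault of wording and consistency. Research Question II sets a post-randomisation subset of one arm against the other arm without restriction, leaves completion undefined, and disagrees with the outcome and analysis sections. The comparison loses the protection of randomisation whatever the sign of the bias.

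The size is not known from the documents. The illustration of 0.05 to 0.16 SD rests on a borrowed non-completion rate, an assumed gap and no baseline adjustment; it can be zero or of opposite sign. Under the further assumptions above, planning the next trial on a completer estimate could give about 61% power in place of 80%, or a trial larger than needed.

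Severity is moderate. The primary feasibility outcomes are untouched, and the harm is confined to the secondary effect estimate and its use in planning.

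**What to change.** 1. Reword Research Question II to compare *parents randomised to the iParent2Parent Program versus parents randomised to waitlist, regardless of the number of calls completed*.
2. State in the Statistical Plan that all randomised parents are analysed in their allocated arm with all available data from months 3 and 6. Those data are already to be collected from both groups; confirm that parents who stop calls still receive the questionnaires.
3. If a completer comparison is wanted, keep it as a labelled supplementary description, with completion defined before the data are seen, and do not use it alone to size the next trial.

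The cost is a few sentences. The sample size stays at 40 and no new data are needed. The one downside is that the reported effect may be slightly smaller than a completer estimate.
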